#### Acute kidney injury of Clavien-Dindo grade II or greater, within 30 days of randomisation

- Equal to 1 if:
  - o acute kidney injury within 30 days of randomisation is Clavien-Dindo II or greater
- Equal to 0 if:
  - o acute kidney injury within 30 days of randomisation is none or Clavien-Dindo I
- · Missing if:
  - o acute kidney injury within 30 days of randomisation is missing

#### Acute cardiac event of Clavien-Dindo grade II or greater, within 24 hours of randomisation

Equal to 1 if:

- At least one of the components of acute cardiac event within 24 hours is Clavien-Dindo II or greater.
- Equal to 0 if:
  - All of the components of acute cardiac event within 24 hours are equal to "None" or Clavien-Dindo I
- Missing if:
  - All components are missing
  - One or more of the components of acute cardiac event within 24 is missing and all other components are "None" or Clavien-Dindo I

#### Acute cardiac event of Clavien-Dindo grade II or greater, within 30 days of randomisation

- Equal to 1 if:
  - At least one of the components of acute cardiac event within 30 days of randomisation is Clavien-Dindo II or greater.
- Equal to 0 if:
  - All of the components of acute cardiac event within 30 days of randomisation are non-missing and equal to "None" or Clavien-Dindo I
- Missing if:
  - All components are missing
  - One or more of the components within 30 days of randomisation is missing and all other components are "None" or Clavien-Dindo I

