#### Secondary outcomes

- Mortality within 180 days of randomisation
- Acute kidney injury of Clavien-Dindo grade II or greater, within 30 days of randomisation
- Acute cardiac event of Clavien-Dindo grade II or greater, within 24 hours of randomisation (safety outcome)
- Acute cardiac event of Clavien-Dindo grade II or greater, within 30 days of randomisation (safety outcome)

Full definitions of secondary outcome measures can be found in the OPTIMISE II protocol.

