#### **General analysis principles**

Analyses will follow the intention-to-treat principle: all randomised patients with a recorded outcome will be included in the analysis, and analysed according to the treatment to which they were randomised (1). Definitions of what constitutes a recorded outcome for each outcome can be found in Appendix 1. Patients with missing outcome data will be excluded from the analysis. Missing data for baseline covariates to be included in the analysis model will be accounted for using mean imputation (2).

For the analysis of the primary outcome, each secondary outcome, and all process measures, we will present the following information:

- The number of patients included in each analysis, by treatment arm
- A summary statistic of the outcome (e.g. number (%)), by treatment arm
- The estimated treatment effect
- A 95% confidence interval for the estimated treatment effect
- A two-sided p-value

For all analyses, a significance level of 5% will be used.

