# Table 10 - Components of acute cardiac events within 24hrs of randomisation

|                                | Complete data |              | Summary measure |            |
|--------------------------------|---------------|--------------|-----------------|------------|
|                                | Intervention  | Usual care – | Intervention    | Usual care |
|                                | – no. (%)     | no. (%)      | (n=)            | (n=)       |
| Arrhythmia                     |               |              |                 |            |
| Myocardial infarction          |               |              |                 |            |
| Myocardial injury after non-   |               |              |                 |            |
| cardiac surgery                |               |              |                 |            |
| Cardiac arrest with successful |               |              |                 |            |
| resuscitation                  |               |              |                 |            |
| Cardiogenic pulmonary oedema   |               |              |                 |            |

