# Table 11 - Components of acute within 30 days of randomisation

|                                 | Complete data |              | Summary measure |            |
|---------------------------------|---------------|--------------|-----------------|------------|
|                                 | Intervention  | Usual care – | Intervention    | Usual care |
|                                 | – no. (%)     | no. (%)      | (n=)            | (n=)       |
| Arrhythmia – no. (%)            |               |              |                 |            |
| Myocardial infarction – no. (%) |               |              |                 |            |
| Myocardial injury after non-    |               |              |                 |            |
| cardiac surgery – no. (%)       |               |              |                 |            |
| Cardiac arrest with successful  |               |              |                 |            |
| resuscitation – no. (%)         |               |              |                 |            |
| Cardiogenic pulmonary oedema    |               |              |                 |            |
| – no. (%)                       |               |              |                 |            |

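### A patient with a recorded grade II or greater cardiac event at 24 hours is coded missing for the 30-day cardiac safety outcome if the 30-day items are incomplete

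*SAP*

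**What the plan says.** SAP section 3 (Secondary outcomes) lists two cardiac safety outcomes, both of Clavien-Dindo grade II or greater and both counted from randomisation: one to 24 hours, the other to 30 days.

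Appendix 1 derives each from its own components:

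- The 24-hour outcome is 1 if "At least one of the components of acute cardiac event within 24 hours is Clavien-Dindo II or greater".
- The 30-day outcome is 1 if "At least one of the components of acute cardiac event within 30 days of randomisation is Clavien-Dindo II or greater".
- The 30-day outcome is 0 if "All of the components of acute cardiac event within 30 days of randomisation are non-missing and equal to 'None' or Clavien-Dindo I".
- The 30-day outcome is missing if every component is missing, or if "One or more of the components within 30 days of randomisation is missing and all other components are 'None' or Clavien-Dindo I".

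The 30-day rule refers neither to the 24-hour components nor to an event date.

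Appendix 5 lists the same five components in two shells, "Table 10 - Components of acute cardiac events within 24hrs of randomisation" and "Table 11 - Components of acute within 30 days of randomisation", each with its own columns for complete data.

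On missing outcomes, section 5 (General analysis principles) states: "Patients with missing outcome data will be excluded from the analysis".

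**The concern.** The two definitions are nested, but the two derivations are not. Once a qualifying event is recorded in the first 24 hours, the 30-day outcome is known to be 1 whatever the 30-day items hold. The missing rule does not use that knowledge, so an incomplete 30-day record removes a patient whose outcome is already settled.

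The SAP itself describes a way in which this could happen. Its missing-data section foresees patients who have gone home and do not answer the 30-day telephone follow-up. Such a patient may have complete 24-hour items.

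At stake is a safety outcome in a trial whose intervention includes an inotrope infusion during surgery and for four hours afterwards. The 30-day outcome also enters the secondary analysis of patients who undergo surgery. The SAP's sensitivity analysis for data missing not at random covers only the primary outcome, so it would not reveal the loss.

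**Working it through.** **Step 1. What the rules allow.** Treat the 24-hour and 30-day components as separate data items, as the separate completeness columns in Tables 10 and 11 suggest. Each set has five components, and each component has three states: None or grade I, grade II or greater, or missing.

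- Patterns per set: 3^5 = 243.
- Scored 1 (any component grade II or greater): 243 − 2^5 = 211.
- Scored 0 (all None or grade I): 1.
- Scored missing: 243 − 211 − 1 = 31. One of these has all components missing; the other 30 are partly missing with the rest None or grade I.

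Crossing the two sets for patients with a 24-hour outcome of 1:

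| 30-day outcome | As written | With a 24-hour event carried forward |
|---|---|---|
| 1 | 211 × 211 = 44,521 | 211 × 243 = 51,273 |
| Missing | 211 × 31 = 6,541 | 0 |
| 0 | 211 × 1 = 211 | 0 |

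These count patterns that the rules permit. They are not probabilities. They show that a 24-hour event can coexist with a missing 30-day outcome, and that carrying the event forward removes every such combination.

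**Step 2. A concrete record.** A grade II arrhythmia is recorded in the 24-hour set, and all five 30-day components are blank. The 24-hour outcome is 1, the 30-day outcome is missing, and the patient leaves the 30-day analysis. Under the section 3 definition the 30-day outcome is 1.

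**Step 3. Scale.** The only planned figure used is the sample size in section 4. It reproduces. For 30% against 25%, two-sided 5% and 80% power, with mean proportion 0.275:

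n per arm = [1.960 × √(2 × 0.275 × 0.725) + 0.842 × √(0.30 × 0.70 + 0.25 × 0.75)]² / 0.05² ≈ 1251, or 2502 in total.

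The SAP states neither a planned 24-hour event rate nor the share of incomplete 30-day items. Both are assumed here: 0.5% to 3%, and 1% to 5%.

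- Patients with a 24-hour event: 2502 × 0.005 ≈ 13, to 2502 × 0.03 ≈ 75.
- Of these, coded missing at 30 days: 2502 × 0.005 × 0.01 ≈ 0.1, to 2502 × 0.03 × 0.05 ≈ 3.8.

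For comparison, an assumed 30-day rate of 15% gives 2502 × 0.15 ≈ 375 events, so the loss is about 0.03% to 1.0% of them. The 15% matches the main prior mean for this outcome in Table A. That is a difference between usual care and no surgery, so it only stands in for an event rate.

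**The case against.** The strongest reply is that the 30-day window includes the first 24 hours. If the 30-day items are completed cumulatively and in full, the rule as written already returns 1 and nothing is lost. The case report form is not shown, and Tables 10 and 11 are output shells that suggest separate items without proving it. This stands: the loss depends on how the data are collected. It does not remove the gap for incomplete records, because the missing rule then applies as written.

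A second reply is that the assumed rates are generous. Table A's 24-hour prior means are 0, 0.01 and 0.02, again as differences from no surgery. Taking 2% as the ceiling lowers the upper figure to 2502 × 0.02 × 0.05 ≈ 2.5. That is fair and bears on severity. Early events also stay visible, since the 24-hour outcome has its own model, its own row in Table 3 and its own component table.

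A reader might go further and infer three things that the SAP does not support.

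- **That an early event is scored as no event at 30 days.** This needs every 30-day item entered as None or grade I despite the earlier event, hence inconsistent entry or items that leave out the first day. The SAP describes neither.
- **That the 30-day comparison is biased towards no harm.** Nothing in the SAP shows that the loss would differ between arms or be large enough to matter.
- **That the overall 30-day count could fall below the 24-hour count.** With about 375 events at 30 days and at most 75 at 24 hours, removing every early event would still leave about 300.

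**Conclusion.** The gap is real but narrow. As written, the 30-day derivation codes as missing, and so excludes, a patient whose 24-hour components already establish the event, whenever the 30-day components are wholly missing or partly missing with nothing of grade II or greater among the rest. This follows from Appendix 1 and the general analysis principles, provided the two component sets are separate items.

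On the assumed rates, about 0.1 to 4 of 2502 patients would be affected, and none if the 30-day items are complete and cumulative. Severity is low. The point is worth correcting because a stated rule would discard known safety events, not because a material shift in the safety comparison has been shown.

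**What to change.** In Appendix 1, under the 30-day acute cardiac event, set the outcome to 1 if any component is Clavien-Dindo grade II or greater in either the 24-hour or the 30-day set. Apply the existing 0 and missing rules only to patients not already scored 1. Build the component rows of Table 11 from both sets in the same way.

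The same rule resolves any discordant record, with an event at 24 hours and none at 30 days, should data entry produce one.

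The cost is one sentence in the SAP and one line of derivation code. No new data are needed, the sample size does not change, and results are unaltered if the two sets already agree.

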#### **Process Measures**

#### **Duration of hospital stay**

This outcome will be defined by two variables, the discharge event (discharged/died before discharge), and time to discharge event.

#### Discharge event

- Patients will be classified as discharged if patient survived to discharge for primary hospital admission.
- Patient will be classified as died before discharge if patient did not survive to discharge for primary hospital admission.
- Discharge event will be missing if item "Did the patient survive to discharge from primary hospital admission?" is missing.

#### Time to discharge event

- Time to discharge event will be equal to the duration of primary hospital admission.
- Time to discharge event will be missing if duration of primary hospital admission is missing or if discharge event is missing.

#### Number of critical care free days up to 30 days from randomisation

- If patient is alive 30 days from randomisation:
  - equal to 30 (total duration of level 2 critical stay within 30 days of randomisation + total duration of level 3 critical stay within 30 days of randomisation)
- If patient died within 30 days of randomisation
  - equal to (date of death date of randomisation) (total duration of level 2 critical stay within 30 days of randomisation + total duration of level 3 critical stay within 30 days of randomisation).
- Missing if:
  - o Total duration of level 2 critical stay within 30 days of randomisation is missing
  - o OR total duration of level 3 critical stay within 30 days of randomisation is missing
  - o Or Mortality at 30 days is missing

# **Appendix 2: Protocol deviations**

The questions used to determine protocol deviations are in section 4 of the main OPTIMISE CRF, titled "Trial intervention period", under the headings "Cardiac output monitoring" and "Drugs".

#### Did not receive cardiac output monitoring (intervention group only)

- Deviation occurs if:
  - "Did the patient receive cardiac output monitoring during the trial intervention period" is answered "No"
- Deviation does not occur if either:
  - "Did the patient receive cardiac output monitoring during the trial intervention period" is answered "Yes"
- Deviation missing if "Did the patient receive cardiac output monitoring during the trial intervention period" is missing

#### Did not receive inotrope (intervention group only)

- Deviation occurs if:
  - o "Inotrope infusion used" is answered "Neither"
- Deviation does not occur if either:
  - o "Inotrope infusion used" is answered either "Dobutamine" or "Dopexamine"
- Deviation missing if "Inotrope infusion used" is missing

#### Received incorrect dose of inotrope (intervention group only)

- Deviation occurs if one of the following holds:
  - $\circ$  "Inotrope infusion used" is answered "Dobutamine" and highest rate administered is greater than 2.7  $\mu$ g/kg/min
  - $\circ$  "Inotrope infusion used" is answered "Dobutamine" and lowest rate administered is less than 2.3 µg/kg/min and "Infusion rate reduced due to tachycardia?" is answered "No"
  - $\circ$  "Inotrope infusion used" is answered "Dopexamine" and highest rate administered is greater than 0.6  $\mu$ g/kg/min
  - $\circ$  "Inotrope infusion used" is answered "Dopexamine" and lowest rate administered is less than 0.4  $\mu$ g/kg/min and "Infusion rate reduced due to tachycardia?" is answered "No"
- Deviation does not occur if one of the following holds:
  - $\circ$  "Inotrope infusion used" is answered "Dobutamine" and highest rate administered is less than 2.7 µg/kg/min and lowest rate administered is greater than 2.3 µg/kg/min
  - "Inotrope infusion used" is answered "Dobutamine" and highest rate administered is less than 2.7 μg/kg/min and lowest rate administered is less than 2.3 μg/kg/min and "Infusion rate reduced due to tachycardia?" is answered "Yes (during surgery)" or "Yes (after surgery)"
  - "Inotrope infusion used" is answered "Dopexamine" and highest rate administered is less than 0.6 μg/kg/min and lowest rate administered is greater than 0.4μg/kg/min

- ° "Inotrope infusion used" is answered "Dopexamine", highest rate administered is less than 0.6  $\mu$ g/kg/min, lowest rate administered is less than 0.4  $\mu$ g/kg/min, and "Infusion rate reduced due to tachycardia?" is answered "Yes (during surgery)" or "Yes (after surgery)"
- Deviation is missing if one of the following holds:
  - Inotrope infusion used is missing
  - Highest rate administered is missing
  - Lowest rate administered is missing and Infusion rate reduced due to tachycardia is not "Yes (during surgery)" or "Yes (after surgery)"
  - $\circ$  Lowest rate administered is less than 2.3 µg/kg/min (dobutamine) or less than 0.4 µg/kg/min (dopexamine) and Infusion rate reduced due to tachycardia is missing

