#### **Table 16 - Protocol deviations**

|                                 | Intervention | Usual care – |
|---------------------------------|--------------|--------------|
|                                 | (n=)         | (n=)         |
| Patients with at least one      |              |              |
| protocol deviation              |              |              |
| Did not receive cardiac output  |              | n/a          |
| monitoring (intervention group) |              |              |
| Did not receive inotrope        |              | n/a          |
| (intervention group)            |              |              |
| Received incorrect dose of      |              | n/a          |
| inotrope (intervention group)   |              |              |
| Received cardiac output         | n/a          |              |
| monitoring (usual care group)   |              |              |

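### The tachycardia exemption in the incorrect-dose rule sets no lower limit on the highest rate, so an infusion that never reached the SAP's own dose band can be counted as no deviation (minor; descriptive tables only)

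*SAP*

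**What the plan says.** The rule is in SAP Appendix 2, under the heading on receiving an incorrect dose of inotrope, and applies to the intervention group only.

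- **Over-dose trigger.** A highest rate above 2.7 µg/kg/min (dobutamine) or 0.6 µg/kg/min (dopexamine) is a deviation.
- **Under-dose trigger.** A lowest rate under 2.3 or 0.4 is a deviation only if "Infusion rate reduced due to tachycardia?' is answered 'No".
- **Exemption, dobutamine.** There is no deviation if the inotrope item "is answered 'Dobutamine' and highest rate administered is less than 2.7", the "lowest rate administered is less than 2.3", and the tachycardia item has either Yes answer ("Infusion rate reduced due to tachycardia?' is answered 'Yes (during surgery)' or 'Yes (after surgery").
- **Exemption, dopexamine.** The same construction is used: "Dopexamine', highest rate administered is less than 0.6", with "lowest rate administered is less than 0.4" and either Yes answer.
- **Missing data.** A missing highest rate makes the deviation missing. A missing lowest rate does so only if the tachycardia answer is not Yes.

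The result feeds the row "Received incorrect dose of" inotrope in Table 16 (Appendix 5), the row for patients with at least one deviation in that table, and the reasons in Table 17.

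**The concern.** The SAP treats 2.3 to 2.7 (dobutamine) and 0.4 to 0.6 (dopexamine) as the band, and a rate outside it counts as incorrect unless excused. The excuse is a CRF item asking whether the rate was reduced because of tachycardia. A reduction can explain why the lowest rate fell under the band. It cannot explain why the highest rate was under the band, because the rate before the reduction can be no greater than the highest rate. The exemption nevertheless passes such an infusion, since no branch compares the highest rate with the lower limit.

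What is at stake is how well Table 16 describes inotrope delivery. The error runs one way: it can remove patients from the incorrect-dose row but never add any. No other planned output recovers them. Table 2 lists the drug used, whether the rate was reduced for tachycardia and the infusion site, but no infusion rates. Appendix 2 also restricts reported reasons to deviations that meet the derived conditions, so a deviation form filed for such a patient would not appear in Table 17.

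**Working it through.** The SAP gives no figure to reproduce here, since the point concerns a classification rule. The check applies the rule as written.

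**Inputs**, all from the incorrect-dose section of Appendix 2: lower limit L = 2.3 and upper limit U = 2.7 for dobutamine; L = 0.4 and U = 0.6 for dopexamine (µg/kg/min). Let H be the highest rate, W the lowest rate and T the tachycardia answer.

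**Rule as written**
- Occurs: H > U, or (W < L and T = No).
- Does not occur: (H < U and W > L), or (H < U and W < L and T = either Yes).
- Missing, among other conditions: W < L and T missing.

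**Logic.** Take W < H < L. Then H < U holds automatically, because L < U. With T = No the under-dose trigger fires. With T = Yes the exemption applies. If R is the rate before the reduction, R ≤ H < L, so the infusion was below the band before anything was reduced.

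**Examples.** The last column adds a check that H is not below L.

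| Drug | H | W | T = No | T = Yes (either) | T = Yes, with check on H |
|---|---|---|---|---|---|
| Dobutamine | 1.5 | 1.0 | occurs | does not occur | occurs |
| Dobutamine | 2.2 | 0.5 | occurs | does not occur | occurs |
| Dobutamine | 2.5 | 1.0 | occurs | does not occur | does not occur |
| Dopexamine | 0.3 | 0.1 | occurs | does not occur | occurs |
| Dopexamine | 0.5 | 0.2 | occurs | does not occur | does not occur |

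**Grid.** All pairs with W < H < L were evaluated under both Yes answers.
- Dobutamine, steps of 0.1: H takes 22 values (0.1 to 2.2), giving 22 × 21 / 2 = 231 pairs, and 231 × 2 = 462 cases. All 462 are classed as no deviation.
- Dopexamine, steps of 0.05: H takes 7 values (0.05 to 0.35), giving 7 × 6 / 2 = 21 pairs, and 21 × 2 = 42 cases. All 42 are classed as no deviation.

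With the check on H, all 462 and all 42 become deviations. Infusions that reached the band and were then reduced (2.5 to 1.0; 0.5 to 0.2) stay excused. These counts show that the gap is complete within the rule; they say nothing about how many patients fall into it.

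**The case against.** The strongest reply is that the text does not contradict itself. Its branches agree that a low rate is a deviation with No and excused with Yes. The sponsor may have meant Yes to excuse any low rate in a patient with tachycardia. The SAP never states the purpose of the exemption, and the dosing instructions belong to the protocol, which is not shown. This stands: the SAP alone cannot establish that such a patient departed from the protocol. It does not remove the point. If the broad reading is intended, the SAP should say so, because the CRF item asks about a reduction and a reduction does not account for the highest rate.

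The consequence is also limited, and that stands too. The SAP plans no per-protocol or adherence-adjusted analysis using this variable. Its one analysis that depends on an event after randomisation concerns undergoing surgery, not inotrope dose. Table 2 also reports how many patients had the rate reduced for tachycardia, by arm. Every exempted patient with an inadequate highest rate is among those Yes answers, so a reader has an upper bound on the undercount, though not the count itself.

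A reader might go further and infer that reported adherence will be too favourable, or that a null result will be hard to interpret. The documents do not support either. Both need such patients to exist in some number, and that requires an infusion kept below the band, then tachycardia, then a further reduction. Nothing in the SAP shows that this happened.

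**Conclusion.** The point holds as a minor defect in a derivation rule. As written, an infusion whose highest rate never reached the SAP's own lower limit is classed as no deviation if the rate was reduced for tachycardia, and as a deviation if it was not. The effect can only lower the incorrect-dose count in Table 16. It lowers the count of patients with at least one deviation only where the patient has no other deviation. The related reasons in Table 17 follow. No treatment estimate, interval or p-value changes.

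The size cannot be derived from the SAP and may be zero. It is tempting to note that 2.3/2.7 = 85% (dobutamine) or 0.4/0.6 = 67% (dopexamine) of the highest rates accepted by the exemption lie below the lower limit. Those are shares of a numerical range, not of patients. A patient count could be produced only by assuming both how often rates were reduced for tachycardia and how many of those infusions were never in band, and the SAP gives neither.

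The conclusion assumes that the limits in Appendix 2 are the band the sponsor wishes to report against. It takes no view on which dose or clinical conduct is right.

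**What to change.** Reconcile the exemption in Appendix 2 with the SAP's existing band and with the protocol's dosing instructions, for classification only. One of two wordings would do:

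1. Let a Yes answer excuse the lowest rate only, and check the highest rate against the existing lower and upper limits for that drug. Add the matching line to the conditions under which a deviation occurs.
2. If Yes is meant to excuse infusions that were never in band, say so and report their number on a separate line of Table 16.

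Under the first option, state whether the check on the highest rate applies only with a Yes answer or whatever the answer. If it applies always, a patient with a highest rate below the lower limit and an unanswered tachycardia item moves from missing to deviation, and the missing-data condition must be reworded to match.

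The cost is a few lines of SAP text and derivation code. No new data are needed, because the highest rate is already a required item in the rule. The downside is that the reported deviation count may rise slightly. No dose or clinical rule is proposed.
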